2.2 Random grouping

The random grouping operation is carried out by using dynamic randomization method of Central stochastic system (network edition). The exactly operation was same as the study 1.

2.3 Blind design and implementation

For the study is the acupuncture treatment, the doctor have to contact the patient directly. It's hard to put blind into practice to doctors. However, the other participants, including patients, observation index recorders, and data statisticians will be implemented blind. They are not aware of the groups of the subjects. At the same time, the subjects will be evaluated by blinding effect.

In order to ensure the better implementation of the blind, the study will provide separate treatment as far as possible for each subject. The measure will do the greatest degree to avoid the discussion between subjects from different groups for the feelings and effects.

2.4 Therapeutic method

The acupuncture needles of the study will be unified with HuaTuo brand disposable acupuncture needles produced by Suzhou Medical Products Factory CO., LTD., and the specifications are $\phi 0.18 \times 25\text{mm}$ and $\phi 0.25 \times 40\text{mm}$. The EA instrument is unified by the acupoint neural stimulator HuaTuo SDZ- II B, which was produced by SuZhou Medical Supplies Co., Ltd.

(1) EA + Carbamazepine group

1) Acupuncture acupoints

Local acupoints:

Main acupoints: The affected side of Si-bai(ST2), Xia-guan (ST7), Di-cang (ST4).

Adjunct acupoints: Quan-liao (SI18) for pain in the 2th branch, Jia-che (ST6) for pain in the 3rd branch and A-shi-xue (Two acupoints will be selected from the second branch or the third one).

Distal acupoints: The two sides of He-gu(LI4) and Wai-guan(TE5).

2) The position of acupoints

According to the 2006 People's Republic of China National Standard (GB/T 12346-2006) "*Acupoints names and positioning*", the position of acupoints is direct as follows.

Si-bai (ST2): On the face, the infraorbital hole.

Xia-guan (ST7): In the face, between the center of the zygomatic arch and the middle of the mandible.

Di-cang (ST4): In the face, next to the corner of the mouth 0.4 cun.

Quan-liao (SI18): In the face, the lower edge of the cheekbones, out corner of eyes straight.

Jia-che (ST6): In the face, a transverse finger (middle finger) above the anterior angle of the mandibular angle.

A-shi-xue: Two points will be selected from the different branches, respectively, between the Xia-guan and Si-bai (the 2th branch), and between the Xia-guan and Di-cang (the 3rd branch).

He-gu (LI4): On the back of the hand, the midpoint of the radial side of the second metacarpal.

Wai-guan (TE5): In the posterior area of the forearm, the distal side of the carpal dorsal distal is 2 inches, and the midpoint of the ulna and the radius.

3) Manipulation

Needling operation: Subjects with supine position, general relaxation, routine

disinfection of the facial skin. The superficial acupuncture will be applied for local points. The tiny needles (0.18×25 mm) will be selected to stimulate the local points with shallow row needling according to the distribution of neuropathy branch of trigeminal neuralgia. The technique should be lightly, the depth should be within 5 mm. It is not required a sense of “Qi” and should not touch the trigger point (the trigger points are the pain sensitive places that light touch can trigger severe pain, such as tiff, cheek, nose and so on. The doctor should have a communication with the subject before needling to clear the position of the trigger, do not needle or touch it.) The He-gu (LI4) and Wai-guan (SJ5) points will be selected as the distal points stimulating with 0.25×40mm needle (20-30mm depth). After the subject has a sense of acid distention (“get Qi”), the reducing method of twirling and lifting-inserting will be applied 10 times. If the subject is feeling pain seriously, the distal acupoints can be needling firstly with reducing method sharply until the pain relief. Then it’s turn to needling the local acupoints .

EA parameters: The Xia-guan (ST7) and Quan-liao (SL18) (or Xia-guan (ST7) and Jia-che (ST6)), He-gu (LI4) and Wai-guan (SJ5) acupoints will be received EA treatment by HuaTuo SDZ- II B acupoint neural stimulator. The EA parameter is a dilute wave with 2/100 Hz, the treatment time is 60 minutes and the current intensity is comfortable to subjects.

4) Oral carbamazepine

Carbamazepine tablets (Jiangsu Pengli Pharmaceutical CO., LTD., 0.1g*100 tablets) should be took orally, 0.1g each time, thrice daily.

5) Frequency, duration and time

Treatment will be performed 3 times per week, and 4 weeks of continuous interventions for a total of 12 times.

(2) EA + Placebo group

In this group, the selection, positioning and manipulation of acupoints, the frequency, duration and retaining needle time of treatment are same as EA + Carbamazepine group; placebo, that appearance and specifications are the same as

carbamazepine, are cooperated taken of dose 0.1g, thrice daily.

(3) Sham EA+ Carbamazepine group

Selection of points and locations: the non-meridional points which are means to the points beside 5-10mm of the real acupoints (avoid the trigger point) in the EA group will be selected and needled with more shallow acupuncture (the depth of needling is about 1-2mm).

The operation of shame EA: The HuaTuo SDZ- II B acupoint neural stimulator with damaged electrode wires will be selected to connect the points next to the Xia-guan(ST7) and Quan-liao (SI18) , He-gu (LI4) and Wai-guan(TE5). The frequency, intensity and retaining time will be same as EA group. The subjects can see the display screen and parameter settings of stimulator, however there is no electricity output in fact.

The dosage and frequency of oral carbamazepine tablets are same as above part.

(4) Sham EA+ Placebo group

The points selection, positioning and manipulation are same as Shame EA+ Carbamazepine group, placebo are cooperated taken of dose 0.1g, thrice daily.

2.5 Emergency treatment

It is forbidden that another analgesic therapies are applied at any time during the trial except the patients continue not pain relief, and seriously affect the daily work and life, can use emergency (add) carbamazepine tablets 0.2 g, once time a day, after a meal. The use date and time and dosage of emergency drugs or other analgesic measures must be recorded in time.

2.6 Therapeutic effects indexes

Subjects are required to write a verifiable diary card to record their pain symptoms in 24 hours every day. The diary includes the following items: (1) daily attack frequency (spontaneous and provoking pain frequency); (2) provoking factors; (3) average pain intensity(VAS) in the past 24 hours; (4) side effect in the past 24 hours (including side effect of drugs or acupuncture); (5) Is there another analgesia therapies have been adopt ? Please record it.

(1) Indexes of main outcome evaluation

- 1) Change from Baseline Intensity of Pain at 6 months (evaluation of the pain by VAS with 0-10 points).
- 2) Change from Baseline Brief introduction of 2-week pain.

Evaluation method: According to pain diary, we will take average data of 2 weeks before treatment (-2~0 week) as baseline, 2 weeks of treatment phase (1~2 week) as data of treatment phase I, 4 weeks of treatment phase (3~4 week) as data of treatment phase II. During the follow-up period, the pain diary card will be continued in the 2 weeks before 3 months (11~12 week)/6 months (23~24 week) after treatments.

(2) Indexes of secondary outcome evaluation

- 1) Brief Pain Inventory-Facial scale (BPI-Facial)
- 2) Patient Global Impression of Change (PGIC)
- 3) Short-Form McGill Pain Questionnaire
- 4) Short- Form 36 Questionnaire

(3) Research cycle and evaluation time points

The treatment periods of this research are 4 weeks, and the follow-up period is 6 months. The above indexes are observed at the time points of baseline (the same day with the grouping and treatment for the subject), treatment period I (the end of the 2nd week), treatment period II (the end of the 4th week), follow-up period I (3rd months after treatment) and follow-up period II (6th months after treatment). The main outcome indexes will be measured weekly (1th week to 4th weeks) during the treatment period.

(4) Safety evaluation and acupuncture expectation evaluation

The relevant safety indicators during the treatment period and during the follow-up period are recorded at any time on the subjects' adverse event records, which is recorded by the acupuncture physician.

- 1) Safety evaluation of electric needle:

The abnormal acupuncture should be record, including broken needle, left needle, fainting, unbearable acupuncture pain (VAS \geq 8 points), local hematoma, infection and abscess. And the symptoms, average degree and average duration of other discomfort

after acupuncture, which refers to the duration of acupuncture 1 hours and above, appear the needle pain, nausea, vomiting, palpitations, dizziness, headache, anorexia and insomnia and other symptoms. Each time the patient is diagnosed and treated, ask if any of the above situations occur. If so, record it immediately.

2) Adverse reaction of carbamazepine:

Blurred or diplopia vision, drowsiness, weakness, nausea, vomiting, mental and/or neurological abnormalities and others.

3) Acupuncture expectation evaluation:

The evaluation is divided to "would be (1 point), not to be (-1 point), not clear (0 point)" to answer the curative effect of acupuncture treatment of CTN and other diseases. Time points: before acupuncture treatment, after acupuncture treatment, follow-up period.

(5) The evaluation of blindness

The subjects will be asked to accept true acupuncture, sham acupuncture or uncertainty. Researchers will compare the percentages of the two groups.

Evaluation time: at the end of the 4th week of any acupuncture treatment.

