2.1 Analysis data set

(1) Full Analysis Set (FAS):

A collection of all randomly assigned and at least one treated case. When analyzing the main therapeutic indicators, the missing values in the FAS set were

transferred to the current (LOCF) method by using the results observed at the latest time point. The Available Case Analysis principle was used in the Analysis of secondary efficacy indicators, general conditions and safety Analysis.

(2) Per Protocol Set (PPS):

Compliance set refers to meet the inclusion criteria and follow the test protocol to complete the treatment of the set of cases, which is consistent with the test protocol, compliance, did not take prohibited drugs, to complete the evaluation of effectiveness (at least the main outcome) cases.

(3) Security Analysis System (SAS):

At least one treatment is received and the actual data of the safety indicator evaluation record is available.

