2.2 Statistical analysis content

The main analysis contents include:

(1) Four groups of cases distribution: Four groups of the total loss rate and the loss due to adverse events off rate comparison.

(2) Comparability analysis: Compare demographic data and other baseline values to measure the comparability of the four groups.

(3) Compliance analysis: The four groups of patients were compared according to the amount of time to receive the appropriate treatment, the program did not use prohibited drugs.

(4) Effectiveness analysis: Main therapeutic indexes are analyzed by PP and ITT simultaneously. Since this study is a multi-center clinical trial, the effect of the central effect and baseline on the therapeutic effect should be taken into account in the analysis.

(5) Effect factor analysis: such as age, gender, duration, combined medication and other factors on the efficacy.

(6) Safety analysis: First, according to the requirements of adverse reaction correlation list describes four groups of adverse events and adverse reactions (including the number of cases of adverse events and laboratory examination indexes before and after the test "normal turn abnormal cases and different rate), statistical

analysis of the adverse reactions by chi-square test.

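### The adverse events compared by chi-square come from the unblinded acupuncture physician, and the blinded patients' diary entries are not tied into that record

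*Combined protocol and SAP*

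**What the plan says.** Protocol section 2.3 accepts that it is "hard to put blind into practice to doctors". It says of the others that they, "including patients, observation index recorders, and data statisticians will be implemented blind".

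Section 2.6(4) says that safety indicators, in treatment and in follow-up, are "recorded at any time on the subjects' adverse event records, which is recorded by the acupuncture physician". The items include needling accidents (broken needle, hematoma, infection and similar) and symptoms such as needle pain, nausea, dizziness and insomnia. The patient is asked about them at each treatment visit.

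The operator cannot avoid knowing the EA arm. In the sham arms, section 2.4(3) uses points 5-10 mm off the real ones, "the depth of needling is about 1-2mm", and an "acupoint neural stimulator with damaged electrode wires will be selected". Real EA goes to within 5 mm at local points and 20-30 mm at distal points.

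Section 2.6 also gives every patient a daily diary. Its item (4) covers side effects of drug or acupuncture over the past 24 hours.

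The SAP sets the safety population in 2.1(3): "At least one treatment is received and the actual data of the safety indicator evaluation record is available". SAP 2.2(6) "describes four groups of adverse events and adverse reactions", with relatedness as part of the listing, and then plans "analysis of the adverse reactions by chi-square test".

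**The concern.** Safety of EA is part of study objective 1, and real versus sham EA is a contrast that the factorial design supports. The record behind that contrast is kept by the one role that the protocol says cannot be blinded. Several listed items are symptoms, so someone must decide whether to enter them. The tested quantity is adverse reactions, so someone must also decide whether an event is related to treatment. Knowledge of the arm can affect both decisions. If sham events are entered less often, EA looks less safe than it is. If EA events are entered less often, a real excess can be missed. A blinded source, diary item (4), is already collected, but the plan gives it no role in the safety comparison.

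**Working it through.** **1. The text side by side**

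| Question | Where | Answer |
|---|---|---|
| Who records safety? | Protocol 2.6(4) | Acupuncture physician |
| Is that person blind to EA versus sham? | Protocol 2.3, 2.4(3) | No |
| Is there a blinded source? | Protocol 2.6, diary item (4) | Yes, the patient |
| Does the SAP bring in the diary for safety? | SAP 2.1(3), 2.2(6) | Not stated |
| Is relatedness judged blind? | Protocol 2.6, 2.7; SAP 2.2(6) | Not stated |
| Is there other verification? | Protocol 2.7 | General wording on training, verification, dedicated staff and monitoring; adverse events and the diary are not mentioned |

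The gap rests on this comparison. The plan gives no figure to reproduce.

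**2. Illustration of size**

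Inputs from the documents: 30 patients per group, four groups (protocol 2.1); two-sided 0.05 (SAP 2.3). Assumed, because the documents give neither: true adverse-reaction rates, and the share of events that are entered.

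Recorded rate = true rate × share entered.

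Four-group Pearson test: X² = Σ 30(p_g − p̄)² / [p̄(1 − p̄)], where p_g is the observed proportion in group g and p̄ is their mean; 3 df; rates found by simulation. Pooled test: 60 real EA versus 60 sham EA, 1 df, no continuity correction, exact enumeration of two binomials.

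*False positives.* True rate 20% in all groups, all EA events entered:

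| Sham events entered | Recorded sham rate | Four-group test | Pooled 60 vs 60 |
|---|---|---|---|
| 100% | 0.20 × 1.0 = 20% | about 5.0% | 5.0% |
| 90% | 0.20 × 0.9 = 18% | 5.3% | 5.8% |
| 80% | 0.20 × 0.8 = 16% | 6.6-6.7% | 8.5% |
| 50% | 0.20 × 0.5 = 10% | 21% | 32.6% |

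*Power.* True rates 30% (EA) and 15% (sham), all sham events entered:

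| EA events entered | Recorded EA rate | Four-group test | Pooled 60 vs 60 |
|---|---|---|---|
| 100% | 0.30 × 1.0 = 30% | 35% | 51% |
| 90% | 0.30 × 0.9 = 27% | 24% | 37% |
| 80% | 0.30 × 0.8 = 24% | 15% | 24% |
| 50% | 0.30 × 0.5 = 15% | about 5% | 5% |

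In the last row the recorded rates are equal, so each test is left with about its nominal 5%.

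The SAP describes four groups and states no pooled EA-versus-sham test. The four-group columns are therefore the closer match to the plan.

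**The case against.** The strongest reply is that the protocol is open about this. Section 2.3 exempts doctors, and the acupuncture physician is that doctor. Section 2.6(4) treats safety separately from the efficacy indexes and names its own recorder, so the blinded index recorders can be read as the people who record efficacy. A reader might infer that 2.3 and 2.6(4) contradict each other. The documents do not support that: safety evaluation does sit under the section on effect indexes, which leaves the scope unclear, but an unclear scope is not a contradiction. This part of the reply stands.

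A second reply is that the plan already limits the bias. The patients who report symptoms are blinded, the same list is asked at each treatment visit, unbearable needling pain has a numeric threshold (VAS of 8 or more), and several items, such as a broken needle or an abscess, can be observed directly. This also stands. It lowers the chance of unequal asking. It does not settle what is entered as other discomfort or what is called a reaction.

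A third reply is that section 2.7 refers to operating procedures and verification. Those procedures are not shown and may cover reconciliation. What is shown is general and does not replace the recorder named in 2.6(4).

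A physician must also record events for immediate care. That is right, and it does not require that the compared data rest on that record alone.

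**Conclusion.** The point holds as a minor gap. An unblinded role supplies the tested safety data, and the documents state neither a link to the blinded diary nor a blinded judgement of relatedness.

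The size is illustrative only. At 80% entry in one arm, the four-group test moves from about 5.0% to 6.6-6.7% false positives, or from about 35% to 15% power. The pooled test would reach 8.5% false positives, but the SAP does not state that test. All of this depends on assumed event rates and entry shares.

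Three stronger inferences are not supported. The documents do not show that recording will differ between arms, or in which direction. The large figures in the tables need half of one arm's events to go unrecorded, and nothing in the documents suggests that. The pain outcome is not touched, because the VAS comes from the patient's own diary. The point is also confined to real versus sham EA: the placebo matches carbamazepine in appearance, and the documents do not say whether the physician knows the drug assignment.

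**What to change.** Keep the physician's record for immediate care. Add to SAP 2.2(6):

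> Before unblinding, a person blind to group (an existing index recorder or data handler) reconciles diary item (4) entries with the adverse event record and judges relation to treatment. The chi-square test uses the reconciled data, and discrepancies are listed by group.

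The listing of discrepancies would show whether recording differed between arms, which the present plan cannot do.

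The cost is a little extra data work; no new form or visit is needed. There are two limits. Some events, such as a hematoma, may hint at the arm to the person who reconciles. In follow-up the diary is stated to continue only for weeks 11-12 and 23-24, so reconciliation there is partial.

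### The acupuncturist, who knows EA or sham assignment, records the symptom reactions that are tested across arms, so EA v sham safety comparisons can be biased

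*Combined protocol and SAP*

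**What the plan says.** Protocol section 2.3 gives direct contact with the patient as the reason why the treating doctor is not blinded: "It's hard to put blind into practice to doctors". It says that the other participants, "including patients, observation index recorders, and data statisticians will be implemented blind", and adds "They are not aware of the groups of the subjects".

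Protocol section 2.6 (4) says that safety indicators are entered at any time during treatment and follow-up on an adverse event record, "which is recorded by the acupuncture physician". Two lists follow. The first covers needle-handling events and symptoms after acupuncture, among them nausea, vomiting, dizziness, headache and insomnia. The patient is to be asked about these at each treatment. The second covers carbamazepine reactions: "Blurred or diplopia vision, drowsiness, weakness, nausea, vomiting, mental and/or neurological abnormalities and others".

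Patients also keep a daily diary (section 2.6), in which item (4) is "side effect in the past 24 hours (including side effect of drugs or acupuncture". In follow-up the diary is described only for weeks 11~12 and 23~24.

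SAP section 2.2 (6) lists adverse events and reactions for the four groups and specifies statistical "analysis of the adverse reactions by chi-square test". The safety of EA is part of objective 1.

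**The concern.** The acupuncturist cannot fail to know the EA assignment. Under section 2.4, sham uses points 5-10 mm away from the real ones, a depth of about 1-2 mm and damaged electrode wires. The same person elicits and records the safety data.

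Some events, such as a broken needle, need the operator. Nausea, dizziness, headache, insomnia and drowsiness do not: they are patient reports, and their capture depends on how they are asked about and what the recorder thinks worth writing down.

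Attribution is exposed too. Nausea and vomiting are on both lists, and no blinded causality review is described. A recorder who knows that the needling was sham may put nausea down to the tablet, and one who knows that it was real may put it down to the needling. Because the SAP tests adverse reactions, this choice could feed directly into the test. Unequal recording can create or hide a difference between arms.

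**Working it through.** **Reading the text**

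1. Recorder of safety data: the acupuncture physician (section 2.6 (4)).
2. Only role described as not blinded: the doctor who gives the treatment (section 2.3).
3. Use of the data: comparison across four groups, with a chi-square test of reactions (SAP 2.2 (6)).
4. Other source from a blinded person: diary item (4). No section names it as a source for the safety analysis or says how it is reconciled with the physician's record.

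These four points establish the route to bias without any calculation.

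**Illustration of size**

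The plan states no figure to reproduce. Inputs from the documents are 30 patients per arm and 120 in total (section 2.1), four groups compared by chi-square (SAP 2.2 (6)), and a two-sided 0.05 level (SAP 2.3). Two inputs are assumptions: the true event rate p, equal in all four arms, and the fraction u of events not recorded in both arms of one EA level.

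Recorded rate in the two affected arms = p × (1 − u). For example, with p = 0.20 and u = 0.50, it is 0.20 × 0.50 = 0.10. The expected recorded count is then 30 × 0.10 = 3 in each affected arm, against 30 × 0.20 = 6 in each of the others.

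Test statistic: X² = Σ 30 × (p̂ⱼ − p̄)² / [p̄(1 − p̄)] over the four arms, with 3 degrees of freedom and critical value 7.815. Here p̂ⱼ is the recorded proportion in arm j and p̄ is the mean over arms.

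The rejection probability is summed exactly over all 31⁴ = 923,521 possible sets of counts:

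| True rate | Equal recording | u = 20% | u = 30% | u = 50% |
|---|---|---|---|---|
| 10% | 4.1% | 4.6% | 5.5% | 9.1% |
| 20% | 4.9% | 6.7% | 9.3% | 20.6% |
| 30% | 5.1% | 8.4% | 13.5% | 34.7% |

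There is no true difference in any row, so every rejection is a false positive. At a 10% rate the expected count is only 30 × 0.10 = 3 per arm even with full recording. The Fisher test that SAP 2.3 allows might then be used, so that row is the least certain guide.

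**The case against.** **Is the blinding statement flatly contradicted?** A reader might infer this, but the documents do not settle it. Section 2.6 uses the word indexes for the main and secondary outcomes, then turns to safety indicators and gives them their own recorder. The blinded index recorders of section 2.3 may therefore be efficacy recorders only. That objection stands: the wording is ambiguous. It does not change who records safety.

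**Are the carbamazepine reactions biased as a whole?** A reader might infer this as well. The stated reason for leaving doctors unblinded is the needling, and the placebo tablet matches carbamazepine in appearance (section 2.4). If the acupuncturist is blind to the tablet, carbamazepine v placebo within the same EA level is largely protected, and that is the main contrast for drug reactions. The protocol does not say whether the acupuncturist is blind to the tablet. The instruction to ask at each treatment also precedes the carbamazepine list, so it is explicit only for needling events.

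**Is the inflation larger?** Pooling to 60 v 60 gives 8.5%, 13.5% and 32.6% at a true 20% rate, and 11.9%, 21.0% and 51.4% at 30%, for the same under-recording. The SAP describes a four-group comparison and specifies no pooled safety test, so these figures should not be used for the plan as written.

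**Are there safeguards?** Yes. Patients are to be blind and keep a side-effect diary, staff at both centres are trained together, specialised data personnel are planned (section 2.7), and asking at every session limits selective capture. These reduce the risk. None replaces the named recorder or makes the diary a source for the test.

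**Conclusion.** The point holds for comparisons that cross EA and sham, including EA plus placebo v sham EA plus carbamazepine, and for the attribution of shared symptoms to needling or drug. Whether it reaches carbamazepine v placebo within an EA level depends on the unstated tablet blinding.

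The plan permits bias; the documents do not show that bias will occur, or in which direction. Under the assumed rates the false-positive risk runs from hardly changed (4.6% v 4.1% with a rare event and 20% under-recording) to severe (34.7% v 5.1% with a 30% rate and 50% under-recording). The calculation assumes equal true rates, independent patients, full recording in the other EA level and 30 analysed per arm.

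The point concerns safety recording and does not bear on the primary pain outcome. It is worth correcting because safety is a stated objective, the test is planned, and the blinded sources largely exist already.

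**What to change.** 1. Keep the acupuncturist's session record, both for events that only the operator can observe and for the full listing of adverse events. Blinded sources should supplement it: the assessments are fewer than the 12 sessions, and the diary has gaps in follow-up.
2. For the between-arm test of symptom reactions, use blinded sources. In the 4-week treatment period, use diary item (4). At the week 2, week 4, month 3 and month 6 assessments, have the existing blinded recorder give a fixed symptom checklist covering the interval since the last assessment.
3. State in section 2.3 whether the blinded recorders cover safety, and whether the acupuncturist is blind to the tablet.
4. Say in the SAP how the session record, diary and checklist are reconciled, and have any attribution to needling or drug that enters the test made by someone blind to the arm.

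The cost is wording in the protocol, case report form and SAP, one short checklist at existing assessments, and modest reconciliation work. No new patients, visits or staff are needed. Blinded capture stays sparser in follow-up, where the diary covers only weeks 11~12 and 23~24 and the checklist relies on recall over months. Both sources depend on patients remaining blind, so the blinding evaluation at the end of week 4 (section 2.6 (5)) should be reported beside the safety comparison.
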